traumatic amnesia, duration of loss of consciousness, and data from initial assessment at Cambridgeshire Community Services, including measures of fluid and crystallised intelligence, dysexecutive syndrome, and frequency of brain injury symptoms (measured via the European Brain Injury Questionnaire). If available, we will additionally collect information on previous diagnosis of depression, as well as any psychological treatments received (e.g., Cognitive Behavioural Therapy) and any pharmacological treatments for depression. This information will be collected from the participant's medical charts. This information will only be collected if the participant has consented to it. If a participant denies access to medical information they will not be denied participation in the main study.

Baseline assessment of all below measures will be collected. Participants will be randomized into one of three conditions: 1) Activity Planning Group; 2) Activity Engagement Group, or 3) Waitlist.

Primary Outcome Measures

There is no primary outcome measure to determine its acceptability and feasibility. Determining these aspects will be based on 1) the post study questionnaire and qualitative data from the exit interviews; 2) the face validity of the intervention materials from participants, and 3) retention of participants within the trial.

The **Behavioural Activation for Depression Scale** (BADS) measures activity theorized to underlie depression according to BA (Kanter, Mulick, Busch, Berlin, & Martell, 2007, Kanter et al., 2009). Overall scores on the BADS will be used to determine the secondary objective of the trial.

Additional Measures

The **Hospital Anxiety and Depression Scale** (HADS; Zigmond & Snaith, 1983) is a widely-used measure of depression and anxiety in clinical settings.

The **Behavioural Inhibition/Behavioural Activation Scales** (BIS/BAS) measures an individual's disposition toward avoiding and engaging in activities (Carver & White, 1994).

The **Intolerance of Uncertainty Scale-Short-Form** (IUS-SF) measures an individual's degree to which they are bothered by uncertainty (Carleton, Norton, & Asmundson, 2007).

The **Impact of Events Scale-Revised** (IES-R) measures acute and routine life stress (Weiss, 2007).

The **Brain Injury Rehabilitation Trust Motivation Questionnaire-Self** (BMQ-S) measures difficulties with overall motivation in ABI (Oddy, Catran, & Wood, 2008).

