The **Motivation for Traumatic Brain Injury Rehabilitation Questionnaire** (MOT-Q) measures level of motivation for rehabilitation-related activities (Chervinsky et al., 1998)

The **Modified Outcome Measure-Participation Objective, Participation Subjective** (MOM-POPS) measures an individual's desired and actual participation in home and community activities (Brown et al., 2004).

The **Sense of Control Scale** (SCS) measures an individual's perceived ability to exert control over their life (Lachman & Weaver, 1998a, 1998b)

The **Credibility/Expectancy Questionnaire** (CEQ) measures participant expectations of treatment outcome and perceived credibility of the treatment (Deville & Borkovec, 2000). This measure will only be given at Time 1.

The **Snaith Hamilton Pleasure Scale** (SHAPS) measures an individuals' ability to experience pleasure in day-to-day activities (Snaith et al., 1995).

The **Fatigue Severity Scale-7** (FSS; Krupp et al., 1989) measures level of fatigue in patient populations.

The **Patient Health Questionnaire-9** (PHQ-9; Kroenke et al., 2001) measures symptoms of depression.

The **Generalized Anxiety Disorder-7 item Scale** (GAD-7; Spitzer et al., 2006) measures symptoms of generalised anxiety disorder such as excessive worry and irritability.

MAPLES Pilot Study for Low Mood in ABI

Neuropsychological Assessment

The below assessment will be used to characterise the population at baseline.

The ***Verbal and Spatial Reasoning Test*** (VESPAR; Langdon & Warrington, 1995) is a fluid intelligence assessment for neurological patients.

Along with the above measures, participants in the Activity Planning Group will be asked to submit a copy of their activity schedules in order to conduct exploratory analyses of what type of activities individuals with an ABI commonly engage in.

The questionnaire battery described above will be administered at baseline (Time 1), post-intervention (Time 2) and 1-month post-intervention (Time 3) either face-to-face, over the phone, via videoconferencing, using online questionnaires or via post, as per convenience for the participant. Participants who are first randomised to the waitlist condition will complete the questionnaire battery again prior to starting in the Activity Planning or Activity Engagement Group.

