Feasibility and practicality of Activity Planning vs. Activity Engagement groups, and each in-person vs. online, will be assessed in three ways: 1) through examining data on attendance and drop out and the occurrence of technical or other barriers (e.g. transport for in-person groups); 2, through a post-study questionnaire administered to all participants, and 3) semi-structured exit interviews. Semi-structured exit interviews will be conducted by a member of the research team that has not administered the intervention or conducted the assessments. Approximately 30% of participants (randomly selected) will be invited to take part in the exit interviews. The interview will cover critical aspects of the trial to ensure success of a full-scale trial, such as utility of content covered in the treatment, whether homework was sufficiently challenging and perceived to be useful, and the impact of the treatment on daily life.

After completing participation in the MAPLES study, participants will be given the option for their contact details to be retained in order to receive a summary of the study results after the results have been published. Additionally, if participants are found not to be eligible OR they have completed their participation in the MAPLES study, they will be given the option to have their contact details retained in order to be contacted about other research studies that may be of interest to them.

Analysis

Quantitative data analysis will be conducted by [name] and supervised by senior members of the research team and by the trial statistical consultant ([name]). First, participants who completed a group in-person will be separated from those who completed their group online in order to compare differences between method of assessment. A general linear model using the BADS across the multiple assessments points will be used to determine the effectiveness of the intervention. In line with our hypotheses, it is predicted that the Activity Planning Group will show improvements in activity level and greater reductions in low mood relative to the Activity Engagement Group and Waitlist group. Effect sizes will be estimated based on the trial data. Exploratory analyses investigating the relationship of the secondary questionnaires to outcome will be conducted using correlation analyses.

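### The secondary objective covers activity and mood, but the plan settles it on an activity score, with no mood scale or arm comparison specified for HA-2; the 1-month Waitlist contrasts also lack an untreated comparator

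*Combined protocol and SAP*

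**What the plan says.** The secondary objective, in the Research Question/Aim(s) table and again under Objectives, is an effect on activity level and on mood compared with a waitlist control. The Hypotheses section splits it into HA-1 (activity) and HA-2 (mood). Each has its own null, and each claims a difference from Waitlist both at post-intervention and at 1 month afterwards.

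Under Primary Outcome Measures, the BADS is said to be a scale that "measures activity theorized to underlie depression according to BA". The same paragraph continues: "Overall scores on the BADS will be used to determine the secondary objective of the trial".

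Among the Additional Measures, two are described in terms of depression. The HADS "is a widely-used measure of depression and anxiety in clinical settings", and the PHQ-9 "measures symptoms of depression". Neither is linked to a hypothesis.

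The Analysis section contains one effectiveness model: "A general linear model using the BADS across the multiple assessments points will be used to determine the effectiveness of the intervention". It then predicts that the Activity Planning Group will do better on activity and show "greater reductions in low mood relative to the Activity Engagement Group and Waitlist group", without naming a mood scale. For the remaining instruments it says: "Exploratory analyses investigating the relationship of the secondary questionnaires to outcome will be conducted using correlation analyses".

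On timing, the Waitlist Group section has these participants wait 8 weeks and then be randomised again to one of the two active groups. The Method section gives them one extra assessment, a second baseline taken before that re-randomisation.

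**The concern.** HA-1 and HA-2 treat activity and mood as separate things to be shown. The premise of the intervention is that raising activity lifts mood, so mood needs its own measurement if that premise is to be examined. If the BADS settles the whole secondary objective, the activity-mood link is assumed rather than tested, and a gain in activity could be published as a gain in mood. If the BADS rule is instead taken not to reach mood, nothing says which depression scale carries HA-2, and that choice stays open until the results are known.

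The 1-month problem is distinct and affects HA-1 just as much. A comparison with Waitlist means something only while Waitlist participants are untreated, and the schedule ends that state after 8 weeks.

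**Working it through.** The documents give no figure to reproduce on this point: no sample size, significance level, effect size or correlation is stated. The check is mainly a comparison of text, followed by counts.

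**Step 1: match each hypothesis to an instrument and an analysis.**

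| Item | HA-1 (activity) | HA-2 (mood) |
|---|---|---|
| Part of the secondary objective (Objectives) | yes | yes |
| Scale assigned (Primary Outcome Measures) | BADS, described as an activity measure | none separately; the BADS sentence covers the objective as a whole |
| Effectiveness model (Analysis) | general linear model on the BADS | none on a mood scale |
| Direct measures collected (Additional Measures) | not needed for this check | HADS, PHQ-9 |
| Analysis named for those measures | not needed for this check | at most exploratory correlation, if they count as secondary questionnaires |

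A correlation between a questionnaire and outcome is not a comparison of arms, so it cannot test HA-2.

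**Step 2: count the mood contrasts.** Two active groups × one time point (post-intervention) = 2 contrasts with Waitlist. The number with a named mood scale or model is 0. Of the 13 Additional Measures (HADS, BIS/BAS, IUS-SF, IES-R, BMQ-S, MOT-Q, MOM-POPS, SCS, CEQ, SHAPS, FSS, PHQ-9, GAD-7), 2 are described as measuring depression.

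**Step 3: are the data there?** Yes. The battery is given at baseline, post-intervention and 1 month, and again to Waitlist participants before they start a group. Post-intervention in the active groups and the second baseline in Waitlist each follow an 8-week period, so the two changes can be compared.

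**Step 4: the 1-month contrasts.** Waitlist participants have four assessments: first baseline, second baseline, post-intervention and 1 month post-intervention. Only the two baselines are untreated. Their own post-intervention visit falls about 8 + 8 = 16 weeks after the wait begins, and the 1-month visit later still (assuming the group starts promptly after the wait), so both follow an active group. The hypotheses imply 2 hypotheses × 2 active groups = 4 Waitlist contrasts at 1 month, with 0 untreated Waitlist assessments to serve them.

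**Step 5: illustration for the looser reading only.** Suppose the better of two mood scales is picked after the fact, each tested two-sided at 5%, with correlation r between the two test statistics. Alpha and r are both assumptions. Under the null, the chance that at least one |Z| exceeds 1.96 is:

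| r | either direction | favouring the active group only |
|---|---|---|
| one pre-named scale | 5.0% | 2.5% |
| 0.8 | 7.8% | 3.9% |
| 0.5 | 9.1% | 4.5% |

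For r from 0.9 to 0.3 the either-direction figure runs from 7.0% to 9.5%. HA-2 is directional, so the last column is the closer description of a false claim of benefit.

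**The case against.** The fairest defence is that this is a feasibility pilot. Its primary objective does not depend on either scale, and the plan promises only to estimate effect sizes from the trial data. That limits the seriousness. It does not remove the point, because the protocol also states directional hypotheses with nulls, randomises to a waitlist and says its model will determine effectiveness.

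Second, the BADS has depression in its name and is tied to the theory of depression. It is fair to call it a depression-related process measure. The protocol's own description, however, is of activity thought to underlie depression, not of mood.

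Third, the opening summary says the waitlist control works by repeating the outcome measures, in the plural, and the effect-size sentence names no outcome, so mood comparisons may well be intended. That is possible, but intention without a named scale is exactly what leaves the choice open.

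Some stronger readings should be resisted:

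- A reader might infer that the plan expressly assigns HA-2 to the BADS. It does not mention HA-2 there; the link follows because HA-2 is the mood half of the objective that the sentence covers.
- A reader might infer that the analysis names no arms. The sentence after the model does name them, for low mood as well as activity. What it lacks is the mood scale and the model.
- A reader might take 7.8% to 9.1% as the size of the defect. It applies only to the looser reading and rests on an alpha and a correlation that the documents do not give.

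**Conclusion.** The point holds and is worth fixing, at the low end of that range. As written, following the plan would report an activity result as the answer on mood. If the BADS rule is read as excluding mood, HA-2 has no pre-specified outcome at all. On either reading both post-intervention mood contrasts lack a named mood scale and model. This rests on the text alone; the false-positive figures are illustrative and do not support the conclusion.

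The 1-month point holds independently: four Waitlist contrasts, across HA-1 and HA-2, have no untreated comparator. It would remain even if a mood scale were named. It does not touch the post-intervention comparison, for which the second baseline provides an untreated Waitlist assessment.

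The primary feasibility objective is unaffected, and the mood data are already scheduled, so nothing is lost if the wording is corrected before the results are examined.

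**What to change.** 1. **Mood outcome.** Under Primary Outcome Measures, limit the BADS sentence to activity (HA-1). For HA-2, name one mood score already in the battery, for example the HADS depression subscale, which already appears in the low-mood entry criterion, with the PHQ-9 as supporting. Under Analysis, fit the same between-arm model to both outcomes, adjusted for the baseline score. Compare the change from baseline to post-intervention in participants first randomised to an active group with the change from first to second baseline in Waitlist. Report each active group against Waitlist as a difference with a 95% confidence interval. A lighter alternative is to label HA-2 exploratory and still limit the BADS sentence to activity.

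2. **1-month comparison.** Remove the 1-month Waitlist comparison from HA-1, HA-2 and both nulls, and limit the 1-month contrast to Activity Planning versus Activity Engagement. The Analysis section already predicts a difference between those two groups, although HA-1 and HA-2 do not state one.

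**Cost.** Revised wording and one further model on data already being collected, with no added visits or questionnaires. There will be a second named outcome, so the two must either be placed in order or both be reported as estimates with intervals. The claim of a 1-month advantage over Waitlist is given up.

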The COVID-19 pandemic has meant that we have had to suspend all in-person contact with research participants. In the current substantial amendment, we are proposing to continue the study using only telephone and on-line contact with participants. Whilst this was not part of our original plan, it does

MAPLES Pilot Study for Low Mood in ABI

offer an opportunity to examine the relative feasibility and acceptability of in-person vs. online videoconferencing groups. This is useful both during the pandemic, whilst social distancing restrictions remain in place, and also afterwards when new means of tele-therapy may have value for patients (e.g. those that find it difficult to travel) and services.

STUDY DESIGN and METHODS of DATA COLLECTION AND DATA ANALYSIS

Trial Design

Activity Planning Group

Generally, those receiving BA training develop and maintain a schedule based on activities that have been enjoyable, pleasant, meaningful, or interesting in the past (Mazzuchelli et al., 2010). Clients are then instructed to monitor their daily mood and participation in these activities to identify the connection between them. Clients are then taught how to increase the frequency and quality of positive events and decrease negative ones (Lewinsohn, 1976; Lewinsohn et al., 1980). In GMT, participants learn how to identify precursors to becoming distracted from their goals and strategies to orient themselves to their environment in order to prevent goal neglect (Levine et al., 2000, 2011).

The intervention will consist of weekly 1 hour group sessions over the course of 8 weeks, covering 8 overarching themes:

- 1) Introduction to Group Therapy
- 2) Identifying Enjoyable Activities
- 3) The Automatic Pilot and Planning Pleasurable Activities
- 4) Goal Review and Balancing Enjoyable and Routine Activities
- 5) Identifying Solutions to Goal Neglect
- 6) Increasing Mastery and Managing Fatigue
- 7) Active Approaches to Engagement
- 8) Relapse Prevention

All sessions will be administered by [name]. Although we have received feedback from individuals with an ABI on the content covered within the Activity Planning Group, if participants within the MAPLES study react negatively to the content covered within the program then such content will be removed from the intervention or restructured so as to not potentially cause distress for future participants.

Activity Engagement Group

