Individuals randomised to the Activity Engagement Group will meet weekly for 8 weeks for 1 hour and engage in various social activities such as board games, crafting, puzzles, similar to the social group in McDonald et al.'s (2008) social arm. Participants in this group will not have specific therapeutic goals and outcomes and will only be encouraged within each session to engage in activities within the group. The group will follow the below schedule:

- 1) Board games
- 2) Shirt Making
- 3) Puzzles
- 4) Painting
- 5) Trivia Day/"Pub Quiz"
- 6) Figurine painting
- 7) Origami/papercraft
- 8) Clay sculptures

MAPLES Pilot Study for Low Mood in ABI

All sessions will be administered by [name]. If participants within the Activity Engagement group strongly oppose engaging in one of the above sessions (e.g., clay sculptures) that session will be replaced with a reasonable substitute (e.g., knitting).

The online versions of the two groups will resemble the in-person groups as closely as possible. Participants will be invited to take part using video-conferencing software. Our plan at the outset is to use GoToMeeting video-conferencing software because it is easy to use, has a number of good security features and does not require participants to sign up for an account. It has also been recommended by our co-sponsor, Cambridge University Hospitals NHS Trust. We will continue to review developments in this area and may switch to an alternative service if there are advantages for data security and ease of use.

In line with the nature of the online groups and restrictions imposed by the COVID-19 crisis, the following changes will be implemented: The Activity Planning Group will focus on activities that fit with current health advice (e.g. that can take place in the home, that do not involve face-to-face contact with others, that fit with current outside home/exercise advice). The Activity Engagement group will focus on verbal games, quizzes and general conversation rather than crafts.

Waitlist Group

Individuals who are randomised to this arm of the trial will be waitlisted for 8 weeks, and then randomised again into either the Activity Planning Group or Activity Engagement Group.

Method

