All participants will complete a baseline assessment, a post-intervention assessment, and a 1-month follow-up assessment. Participants in the waitlist group will complete an additional baseline assessment prior to being re-randomised into either the Activity Planning Group or the Activity Engagement.

Randomisation Procedure

The MAPLES study will use pre-determined randomisation. Prior to any recruitment, [name] (Departmental Statistician) will generate a randomisation sequence known only to him in which the condition allocation of each consecutive consenting participant will be listed. These will be placed in sealed envelopes showing only the participant number. After conducting a baseline assessment, the researcher ([name]) will simply open the next envelope in the sequence. In order to maintain approximate parity in group size across the duration of the study (e.g. such that participants recruited later are not more likely to appear in one or other condition and such that the groups are approximately balanced at any point of study termination) randomisation will occur in subblocks of varying lengths. The researcher will not know the length of the current block over which randomisation has been balanced such that she could guess that, e.g. if the last 3 allocations had been to condition A, the next was bound to be B. At the outset of the study, [name] will similarly create randomised sequence that will determine to which of the two intervention groups each participant initially randomised to the wait-list condition will be allocated after the wait period. Again, these will be balanced over variable length subblocks and will be opened in order by the researcher after completing the second baseline assessment with Waitlist participants. In this manner, randomisation is conducted blind to any information about the participants and cannot influence or be influenced by the results of baseline assessments.

Baseline and Outcome Measures.

Demographic information will be collected from participants, including months since injury, type and cause of injury (e.g., non-TBI, hypoxia), comorbidities, Glasgow Coma Scale Scores, length of post-

MAPLES Pilot Study for Low Mood in ABI

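### Activity schedules come only from the Activity Planning Group, during treatment, so they cannot show what activities people with ABI usually do

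*Combined protocol and SAP*

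**What the plan says.** Under Neuropsychological Assessment the protocol states that "participants in the Activity Planning Group will be asked to submit a copy of their activity schedules", and gives the reason as "in order to conduct exploratory analyses of what type of activities individuals with an ABI commonly engage in". No other arm is asked for schedules, and the Analysis section gives no method for them.

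The Activity Planning Group section explains where the schedules come from. In behavioural activation generally, "those receiving BA training develop and maintain a schedule based on activities that have been enjoyable, pleasant, meaningful, or interesting in the past". It continues: "Clients are then taught how to increase the frequency and quality of positive events and decrease negative ones". Themes 2 to 4 of the eight weekly sessions deal with choosing, planning and balancing activities.

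The paragraphs on the online versions, at the end of the Activity Engagement Group section, add that "The Activity Planning Group will focus on activities that fit with current health advice".

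Under Additional Measures, the MOM-POPS "measures an individual's desired and actual participation in home and community activities". It belongs to the questionnaire battery given at Times 1, 2 and 3. The Method section says: "All participants will complete a baseline assessment, a post-intervention assessment, and a 1-month follow-up assessment". Under Randomisation Procedure, the allocation envelope is opened only after baseline. The one analysis stated for the secondary questionnaires is their correlation with outcome.

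**The concern.** The question concerns usual behaviour in a population: what people with ABI commonly do. The chosen source is a treatment document from one arm. If the treatment works as intended, the activities on the schedules will differ from those the same people would otherwise have done. HA-1 predicts exactly such a change in activity level relative to the Waitlist. A record made while activity is being deliberately altered cannot also serve as the record of usual activity.

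What is at stake is one exploratory description. Followed as written, the plan would answer its own question with activities shaped by the treatment and, online, by the group's focus on what health advice permitted.

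**Working it through.** The protocol states no figure for this point, so the check is mainly a comparison of its sections.

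**What each source can show**

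| | Activity schedules | Time 1 MOM-POPS |
|---|---|---|
| Who supplies it | Planning Group, including Waitlist participants later allocated to it | All participants |
| When | Within the programme | Before the envelope is opened |
| Influence of treatment | Direct: scheduling is part of the treatment | None |
| Influence of the pandemic | Online content focused on activities that fit health advice | Online-phase assessments reflect the same conditions, but without direction by the group |
| Population | ABI with low mood | ABI with low mood |
| Stated use | Description of common activities | Correlation with outcome |

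The schedules differ from the stated question in two ways that the Time 1 MOM-POPS does not: they come from one intervention, and they are made on treatment. Both sources share the low-mood restriction, which comes from the inclusion criteria, and the general effect of the pandemic.

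**Coverage**

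The allocation ratio is not given. Randomisation Procedure says only that group sizes are kept roughly equal, using sub-blocks of varying length. I assume 1:1:1 at first allocation and 1:1 when the Waitlist is re-randomised.

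- Share allocated to Planning at first: 1/3.
- Share allocated to Planning through the Waitlist: 1/3 × 1/2 = 1/6.
- Share who could ever supply a schedule: 1/3 + 1/6 = 1/2.

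The proportion able to submit is therefore 1/3 from first allocation alone, rising to 1/2 if every re-randomised Waitlist participant takes up the allocated place. Participants who do not hand in a schedule reduce it further. Every schedule comes from after the programme has begun, including those of former Waitlist participants.

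Time 1 MOM-POPS is planned for everyone. That too is an upper limit, because the Protocol compliance section expects some assessments to be only partly completed.

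**The case against.** The strongest reply is that this is half a sentence, loosely worded, about work labelled exploratory. It serves no stated objective, hypothesis or feasibility criterion, and no estimate or test depends on it. That stands, and it sets the severity.

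Further points stand in part:

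- A reader might infer that the schedules record intentions only. The Activity Planning Group section says that clients also monitor their participation, and theme 4 includes routine activities. Schedules may therefore record things actually done, although still during treatment.
- A reader might infer that the result would overstate enjoyable or home-based activities. The schedule form is not in the documents, and the online guidance also allows for activity outside the home. The direction of any distortion cannot be shown.
- A reader might infer that the full-scale trial would be given the wrong activity content. The documents link the exit interviews, not the schedules, to a full-scale trial, so this is conjecture.
- MOM-POPS is known here from a single descriptive line. Its items are not shown, so it may not give activity types in as much detail as a schedule. It is also not idle, since correlations with outcome are planned.
- Time 1 MOM-POPS describes ABI with low mood, not ABI in general, and in the online phase it describes life under restrictions.
- The Analysis section already separates in-person from online participants, so that part of the remedy only needs extending to the schedules and the new table.

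None of this makes on-treatment schedules a record of usual activity.

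**Conclusion.** The point holds at low severity. Schedules supplied only by Planning Group participants, within a programme designed to change activity, cannot support a statement about what people with ABI commonly do. They can support a description of what was scheduled or carried out during the intervention.

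Under the assumed ratios, at most about half of participants could ever supply a schedule, whereas Time 1 MOM-POPS is planned for all. A reader might go on to claim that MOM-POPS would at least double the sample. That does not follow: both figures are upper limits, and the documents give neither completion rates nor a sample size. Nor does coverage measure the distortion. The conclusion rests on how the schedules arise, not on the fraction.

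MOM-POPS is the better available source because it is untreated and is planned for every arm. How far it can answer the question depends on items that the documents do not show. The feasibility objective and the BADS comparison are unaffected.

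**What to change.** 1. Under Neuropsychological Assessment, restate the purpose of the schedules as describing the activities that Planning Group participants scheduled or carried out during the intervention. Report them separately for in-person and online groups, with the number of participants who submitted one.
2. In the Analysis section, add a descriptive table of Time 1 MOM-POPS in all randomised participants, split by in-person and online phase and showing the number with usable data. Use this table for any statement on usual activity.
3. Limit that statement to people with ABI and low mood, and to the level of detail that the MOM-POPS items allow. Check the items before committing to activity categories.

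The cost is a wording change and one extra descriptive table from data already planned. No new measure, visit or participant burden is involved.
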